4.6 Blinding/Unblinding

Blinding of treatment assignment is critical to the integrity of this clinical study. However, in the event of a medical emergency or pregnancy in an individual subject in which knowledge of the investigational product is critical to the subject's management, the blind for that subject may be broken by the investigator. The subject's safety takes priority over any other considerations in determining if a treatment assignment should be unblinded.

Before breaking the blind of an individual subject's treatment, the investigator should determine that the unblinded information is necessary, ie, that it will alter the subject's immediate management. In many cases, particularly when the emergency is clearly not related to the investigational product, the problem may be properly managed by assuming that the subject is receiving active product. It is highly desirable that the decision to unblind treatment assignment be discussed with the Medical Monitor, but the investigator always has ultimate authority for the decision to unblind. The Principal Investigator should only call in for emergency unblinding AFTER the decision to discontinue the subject has been made.

For this study, the method of unblinding for emergency purposes is the Central Randomization System (IVRS/IWRS).

In cases of accidental unblinding, the Medical Monitor should be contacted and every attempt should be made to preserve the blind.

Any request to unblind a subject for non-emergency purposes should be discussed with the Medical Monitor.

The BMS Bioanalytical Science Department or its designee will be unblinded to the randomized treatment assignments in order to accurately perform sample analysis for the PK and Immunogenicity samples.

4.7 Treatment Compliance

All subjects are expected to receive study therapy as outlined in the protocol. Subjects will use diary cards to document self-injection of study drug between clinic visits. Permitted dose modifications are described in [Section 4.5.2](#). Conditions under which therapy must be discontinued due to non-compliance are outlined in [Section 3.5](#).

4.8 Destruction or Return of Investigational Product

For this study, IP (those supplied by BMS, a vendor or sourced by the investigator) such as partially used study drug containers, vials and syringes may be destroyed on site.

If...	Then...
IP supplied by BMS (including its vendors)	Any unused IP supplied by BMS can only be destroyed after being inspected and reconciled by the responsible Study Monitor unless IP containers must be immediately destroyed as required for safety, or to meet local regulations (eg, cytotoxics or biologics). If IP will be returned, the return will be arranged by the responsible Study Monitor.
IP sourced by site, not supplied by BMS (or its vendors) (examples include IP sourced from the sites stock or commercial supply, or a specialty pharmacy)	It is the investigator's or designee's responsibility to dispose of all containers according to the institutional guidelines and procedures.

It is the investigator's or designee's responsibility to arrange for disposal, provided that procedures for proper disposal have been established according to applicable federal, state, local, and institutional guidelines and procedures, and provided that appropriate records of disposal are kept. The following minimal standards must be met:

- On-site disposal practices must not expose humans to risks from the drug
- On-site disposal practices and procedures are in agreement with applicable laws and regulations, including any special requirements for controlled or hazardous substances
- Written procedures for on-site disposal are available and followed. The procedures must be filed with the site's SOPs and a copy provided to BMS upon request
- Records are maintained that allow for traceability of each container, including the date disposed of, quantity disposed, and identification of the person disposing the containers. The method of disposal, ie, incinerator, licensed sanitary landfill, or licensed waste disposal vendor must be documented
- Accountability and disposal records are complete, up-to-date, and available for the Monitor to review throughout the clinical trial period

It is the investigator's or designee's responsibility to arrange for disposal of all empty containers.

If conditions for destruction cannot be met the responsible Study Monitor will make arrangements for return of IP provided by BMS (or its vendors). Destruction of non-IP sourced by the site, not supplied by BMS, is solely the responsibility of the investigator or designee.

Please refer to [Section 9.2.2](#) for additional guidance on IP records and documentation.

4.9 Retained Samples for Bioavailability / Bioequivalence

Not Applicable.

Table 5.1-1: Screening Procedural Outline (IM101603)

Procedure	Screening Visit ^a	Screening Visit 2 ^b	Notes
Urinalysis	X		
HBsAg, anti-HBcAb (anti-HBsAb where required)	X		If positive, obtain HBV DNA (see Section 5.3.7.5)
Hepatitis C Antibody	X		If positive, reflex to HCV confirmation such as PCR
HIV	X		Testing performed locally, if required
Anti-Ro Antibody (anti-SSA)	X		
Quantitative Immunoglobulins (IgG, IgA, IgM)	X		
Urine/Serum Pregnancy Test	X	X	WOCBP only, see Appendix 1 for details
Disease Assessments			
ESSDAI	X	X	
Stimulated Salivary Flow	X	X	See Section 5.4.2

^a The duration of the screening period should not exceed 28 days.

^b Subjects that experience an acute infection or initiate treatment for latent TB may extend the screening period to 56 days. Under these circumstances, all screening procedures except subject consenting, IVRS enrollment, height/weight, immunoglobulins, urinalysis, chest x-ray, TB testing, HepB/C and HIV should be repeated prior to randomization.

Table 5.1-2: Double-Blind Treatment Period - Procedural Outline (IM101603)^{a,b}

Procedure	Day 1	Day 29 (Wk 4)	Day 57 (Wk 8)	Day 85 (Wk 12)	Day 113 (Wk 16)	Day 141 (Wk 20)	Day 169 (Wk 24)/ Early Term.	Notes
Quantitative Immunoglobulins (IgG, IgM, IgA)	X	X		X	X		X	
hsCRP	X	X	X	X	X	X	X	
ESR	X	X	X	X	X	X	X	Performed locally, kits provided centrally.
Rheumatoid Factor, IgM-RF	X	X		X	X		X	
β-2-Microglobulin (B2M)	X	X		X	X		X	
Free Light Chain (FLC)	X	X		X	X		X	
Complement (C3, C4, CH50)	X	X		X	X		X	
Anti-Ro Antibody (anti-SSA)	X	X		X	X		X	
Anti-La Antibody (anti-SSB)	X	X		X	X		X	
Anti-centromere Antibody (ACA)	X	X		X	X		X	
Anti-CCP2	X	X		X	X		X	
	L			L			L	
	L						L	
	L			L			L	
	L							
	L						L	
	L			L			L	

Table 5.1-2: Double-Blind Treatment Period - Procedural Outline (IM101603)^{a,b}

Procedure	Day 1	Day 29 (Wk 4)	Day 57 (Wk 8)	Day 85 (Wk 12)	Day 113 (Wk 16)	Day 141 (Wk 20)	Day 169 (Wk 24)/ Early Term.	Notes
Pharmacokinetic (PK) Assessments								
Pharmacokinetic (PK) Sampling	X	X	X	X	X	X	X	Samples collected predose, except for ET. See additional PK sampling for PK sub-study (Table 5.1-5). See more details in Section 5.5.1 .
Immunogenicity (anti-abatacept antibody) testing	X			X			X	Samples collected pre-dose See more details in Section 5.5.1 . Subjects who discontinue treatment with the study drug will require a visit to assess safety and immunogenicity 28 and 84 days after the last dose of study drug. If the visit is within ± 14 days of a scheduled study visit, only an additional laboratory assessment for immunogenicity needs to be performed at the scheduled visit.
Efficacy Assessments								
ESSDAI	X	X	X	X	X	X	X	

Table 5.1-2: Double-Blind Treatment Period - Procedural Outline (IM101603)^{a,b}

Procedure	Day 1	Day 29 (Wk 4)	Day 57 (Wk 8)	Day 85 (Wk 12)	Day 113 (Wk 16)	Day 141 (Wk 20)	Day 169 (Wk 24)/ Early Term.	Notes
Tender (68)/Swollen (66) Joint Count	X	X	X	X	X	X	X	
Physician's Global Assessment of Disease Activity	X	X	X	X	X	X	X	
ESSPRI	X	X	X	X	X	X	X	
PROMIS Fatigue	X	X	X	X	X	X	X	
Subject's Global Assessment of Disease Activity	X	X	X	X	X	X	X	
Mouth (Oral) Dryness (NRS)	X	X	X	X	X	X	X	
Eye (Ocular) Dryness (NRS)	X	X	X	X	X	X	X	
SF-36	X			X			X	
Female Sexual Function Index (FSFI)	X			X			X	
Unstimulated Salivary Flow	X			X			X	See Section 5.4.2
Stimulated Salivary Flow	X			X			X	See Section 5.4.2
Schirmer Test ^c	X			X			X	
Tear Break-Up Time ^c	X			X			X	
Ocular Staining Score ^c	X			X			X	
Study Drug								
Contact IVRS/IWRS	X	X	X	X	X	X		
Train subjects and/or caregiver on how to self-inject and how to fill out the diary cards	X							
Dispense diary cards	X	X	X	X	X	X		

Table 5.1-2: Double-Blind Treatment Period - Procedural Outline (IM101603)^{a,b}

Procedure	Day 1	Day 29 (Wk 4)	Day 57 (Wk 8)	Day 85 (Wk 12)	Day 113 (Wk 16)	Day 141 (Wk 20)	Day 169 (Wk 24)/ Early Term.	Notes
Collect and review diary cards		X	X	X	X	X	X	
Dosing of weekly abatacept/placebo	X	X	X	X	X	X		Must be administered weekly between visits. See Section 4.5 No dose administered at the Early Termination visit
Dispense monthly abatacept/placebo	X	X	X	X	X	X		
Reconciliation of abatacept/placebo monthly kits		X	X	X	X	X	X	

^a All visits and procedures during the Double-Blind Treatment Period must occur within ± 3 days of the expected visit

^b All subjects who discontinue study drug during the double-blind period should continue to comply with protocol specified procedures as outlined in [Table 5.1-2](#). The only exception to this requirement is when a subject withdraws consent for all study procedures including post-treatment study follow-up or loses the ability to consent freely (i.e., is imprisoned or involuntarily incarcerated for the treatment of either a psychiatric or physical illness).

^c Procedure to be performed by an ophthalmologist or optometrist experienced in the diagnosis and treatment of Sjögren’s syndrome patients. Eye assessments must be performed within ± 5 days of the study visit. See [Section 5.4.3](#) for additional detail.

Table 5.1-3: Open-Label Treatment Period Procedural Outline (IM101603)^a

Procedure	Day 169 (WK 24) ^b	Day 197 (Wk 28)	Day 225 (Wk 32)	Day 253 (Wk 36)	Day 281 (Wk 40)	Day 309 (Wk 44)	Day 337 (Wk 48)	Day 365 (Wk 52)/ End of Treatment	Notes
ESR		X	X	X	X	X	X	X	Performed locally, kits provided centrally.
Rheumatoid Factor; IgM-RF				X				X	
Free Light Chain (FLC)				X				X	
β-2-Microglobulin (B2M)				X				X	
Complement (C3, C4, CH50)				X				X	
Anti-Ro Antibody (anti-SSA)				X				X	
Anti-La Antibody (anti-SSB)				X				X	
Anti-centromere Antibody (ACA)				X				X	
Anti-CCP2				X				X	
Pharmacokinetic (PK) Assessments									
Pharmacokinetic (PK) Sampling								X	No sample collection at EOT.
Immunogenicity (anti-abatacept antibody) testing								X	No sample collection at EOT.
Biomarker Assessments									
Serum Biomarkers				X				X	See Section 5.6.3
Saliva Biomarkers				X				X	See Section 5.6.4
Blood Immunophenotyping								X	See Section 5.6.5
PBMCs				X				X	See Section 5.6.5

Table 5.1-3: Open-Label Treatment Period Procedural Outline (IM101603)^a

Procedure	Day 169 (WK 24) ^b	Day 197 (Wk 28)	Day 225 (Wk 32)	Day 253 (Wk 36)	Day 281 (Wk 40)	Day 309 (Wk 44)	Day 337 (Wk 48)	Day 365 (Wk 52)/ End of Treatment	Notes
Efficacy Assessments									
ESSDAI		X	X	X	X	X	X	X	
Tender (68)/Swollen (66) Joint Count		X	X	X	X	X	X	X	
Physician's Global Assessment of Disease Activity		X	X	X	X	X	X	X	
ESSPRI		X	X	X	X	X	X	X	
PROMIS Fatigue		X	X	X	X	X	X	X	
Subject's Global Assessment of Disease Activity		X	X	X	X	X	X	X	
Mouth (Oral) dryness (NRS)		X	X	X	X	X	X	X	
Eye (Ocular) dryness (NRS)		X	X	X	X	X	X	X	
SF-36				X				X	
Female Sexual Function Index (FSFI)				X				X	
Unstimulated Salivary Flow				X				X	
Stimulated Salivary Flow				X				X	
Schirmer Test ^c				X				X	
Tear break-up time ^c				X				X	
Ocular staining score ^c				X				X	

Table 5.1-3: Open-Label Treatment Period Procedural Outline (IM101603)^a

Procedure	Day 169 (WK 24) ^b	Day 197 (Wk 28)	Day 225 (Wk 32)	Day 253 (Wk 36)	Day 281 (Wk 40)	Day 309 (Wk 44)	Day 337 (Wk 48)	Day 365 (Wk 52)/ End of Treatment	Notes
Study Drug									
Contact IVRS/IWRS	X	X	X	X	X	X	X		
Dispense diary cards	X	X	X	X	X	X	X		
Collect and review diary cards		X	X	X	X	X	X	X	
Dosing of weekly abatacept	X	X	X	X	X	X	X		Must be administered weekly between visits. See Section 4.5 No dose administered at the End of Treatment visit
Dispense monthly abatacept kits	X	X	X	X	X	X	X		
Reconciliation of abatacept monthly kits		X	X	X	X	X	X	X	

^a All visits and procedures during the Open-label Treatment Period must occur within ± 3 days of the expected visit

^b Same Day as Double-Blind Day 169

^c Procedure to be performed by an ophthalmologist experienced in the diagnosis and treatment of Sjögren’s syndrome patients. Eye assessments must be performed within ± 5 days of the study visit.

Table 5.1-6: Follow-Up Period Procedural Outline for IM101603 (After Last Dose of Study Medication)^a

Procedure	28 Days	84 Days	Notes
Adverse Events Assessment	X	X	
Laboratory Tests			
Urine/Serum Pregnancy	X	X	
Serum anti-abatacept antibodies	X	X	
Pharmacokinetic (PK) Sampling ^b	X	X	

^a These visits should occur 28 and 84 days after the last dose of study medication. If study medication is discontinued during the Double-Blind Treatment Period and the subject continues to be followed for the scheduled Double-Blind Treatment Period visits these additional visits may not be required.

^b The samples for PK will be evaluated to determine serum abatacept concentration in the event there is a corresponding positive immunogenicity result

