3.1.4 Post-Treatment Follow-up Period

Subjects who discontinue treatment of study drug during the open-label period or complete the study will have two follow-up visits 28 and 84 days after the last treatment visit, to perform safety and laboratory assessments, including immunogenicity testing. Subjects who discontinue treatment with the study drug during the double-blind period will require two visits to assess safety and immunogenicity 28 and 84 days after the last dose of study drug. If these visits are within ± 14 days of a scheduled study visit, only an additional laboratory assessment (immunogenicity) needs to be performed at the scheduled study visit. Otherwise, the follow-up visits as described in the Time & Events table ([Table 5.1-6](#)) need to be performed.

The start of the trial is defined as the date the first subject signs the informed consent. End of trial is defined as the last visit or scheduled procedure shown in the Time & Events schedule for the last subject. The study will continue beyond primary endpoint collection until the End of Trial.

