3.5 Discontinuation of Study Therapy

Subjects who discontinue treatment with investigational product during the Double-Blind Treatment Period must continue to be assessed for all efficacy measures and for safety at all remaining double-blind study visits through Week 24 (Day 169) (see [Table 5.1-2](#)). Those subjects who discontinue treatment with the study drug during the double-blind period will also require visits to assess safety and immunogenicity at 28 and 84 days after the last dose of study drug. If these visits fall within ± 14 days of a scheduled double-blind study visit, only an additional laboratory assessment (immunogenicity) needs to be performed at the scheduled study visit. Otherwise, the follow-up visits need to be performed.

Subjects who discontinue study drug during the Open-Label Treatment period should comply with protocol specified follow-up procedures as outlined in [Section 5](#). The only exception to this requirement is when a subject withdraws consent for all study procedures including post-treatment study follow-up or loses the ability to consent freely (ie, is imprisoned or involuntarily incarcerated for the treatment of either a psychiatric or physical illness).

Subjects MUST discontinue investigational product (and non-investigational product at the discretion of the investigator) for any of the following reasons:

- Subject's request to stop study treatment
- Any clinical adverse event (AE), laboratory abnormality or intercurrent illness which, in the opinion of the investigator, indicates that continuation of study therapy is not in the best interest of the subject
- Pregnancy
- Missed Doses:
 - During the double-blind period, any subject who misses greater than four consecutive doses or greater than eight total doses must be discontinued from study therapy
 - During the open-label period, any subject who misses greater than six consecutive doses or greater than ten total doses must be withdrawn from the study
- Significant non-compliance with protocol (ie, procedures, assessments, medication, etc). The investigator should discuss such issues with the BMS Medical Monitor.
- Use of prohibited medication. The investigator should discuss the use of a prohibited medication with the Medical Monitor prior to withdrawing a subject from study therapy

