5.5 Pharmacokinetic Assessments

5.5.1 Pharmacokinetic: Blood Collection

The sampling schedule to be followed for the assessment of pharmacokinetics is listed in [Table 5.5.1-1](#). The actual date and time of sample collection should be recorded. Every effort should be made to collect PK samples as close to the protocol-specified times as possible.

All randomized subjects will have PK samples collected during the Double-Blind Treatment Period, Open-Label Treatment Period and the Post-Treatment Follow-up Period unless the subject discontinues study treatment and starts treatment with commercial abatacept.

In addition, approximately 40 randomized subjects (approximately 20 subjects randomized to active treatment and 20 subjects randomized to placebo) will participate in a PK sub-study. Those subjects that sign consent to participate in the PK sub-study will have samples collected Days 2, 5, 15, 17, 32, and 61 (see [Table 5.5.1-1](#)). Each sub-study visit may be a home visit conducted by a visiting nurse or qualified healthcare professional if approved by the IRB/IEC and investigator.

Table 5.5.1-1: Pharmacokinetic (PK) Sampling Schedule

Study Day	Event	Time (Relative to Dosing) Hour:Min	PK Blood Sample		Immunogenicity Sample
			All Subjects (N=144)	For PK sub-study (N = 40)	All Subjects (N=144)
1	predose	0	X		X
2		24:00		X	
5		96:00		X	
15	predose	0		X	
17 ± 1		24:00 to 72:00		X	
29	predose	0	X		
32 ± 1		48:00 to 96:00		X	
57	predose	0	X		
61 ± 1		72:00 to 120:00		X	
85	predose	0	X		X
113	predose	0	X		
141	predose	0	X		
169 or ET ^a	predose	0	X		X
365 or EOT ^a			X		X
Post-Treatment Follow-up Period ^b					
28		696:00 hrs	X ^c		X ^d
84		2016:00 hrs	X ^c		X ^d

[figure not shown]
^a Sample collected predose, except for Early Termination (ET) and End of Treatment (EOT).

[figure not shown]
^b Only for subjects discontinuing use of abatacept (off study).

^c These samples will only be evaluated to determine serum abatacept concentration in the event there is a corresponding positive immunogenicity result.

^d These samples should be collected 28 and 84 days after the last dose of study medication. If study medication is discontinued during the Double-Blind Treatment Period and the subject continues to be followed for the scheduled Double-Blind Treatment Period visits these additional samples may not be required.

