5.8 Other Assessments

5.8.1 Immunogenicity Assessments

5.8.1.1 Immunogenicity: Blood Collection

Blood samples for determination of antibodies to abatacept, and time-matched PK samples will be collected at times noted in [Section 5.5.1](#). Samples MUST be collected prior to the administration of study medication (SC injections) based on the collection schedule except during the Follow-up Period. Samples will be assayed for the presence of abatacept-specific antibodies.

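### The protocol gives conflicting instructions on two antibody collections: the end-of-treatment sample and the 28- and 84-day samples after double-blind discontinuation

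*Protocol*

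**What the plan says.** **End-of-treatment sample.** In Protocol Table 5.1-3, the PK and immunogenicity rows each carry an X under Day 365/End of Treatment, and each has the note "No sample collection at EOT". Table 5.5.1-1 has a row for Day 365 or EOT with an X for both samples. Its footnote a reads "Sample collected predose, except for Early Termination (ET) and End of Treatment (EOT", so EOT is exempt only from the predose timing. Section 5.8.1.1 says: "Blood samples for determination of antibodies to abatacept, and time-matched PK samples will be collected at times noted in" section 5.5.1.

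**Samples after double-blind discontinuation.** Section 3.5 says these subjects "will also require visits to assess safety and immunogenicity at 28 and 84 days after the last dose of study drug", on top of their remaining double-blind visits. If a follow-up visit falls within 14 days of a regular visit, section 3.1.4 lets the two be merged but keeps the blood draw: "only an additional laboratory assessment (immunogenicity) needs to be performed at the scheduled study visit". The immunogenicity note in Table 5.1-2 agrees: "only an additional laboratory assessment for immunogenicity needs to be performed at the scheduled visit". Section 5.3 also asks early terminators to complete the follow-up visits. Against this, footnote d of Table 5.5.1-1 says that, for subjects still attending double-blind visits, "these additional samples may not be required". Footnote a of Table 5.1-6 says of the same subjects "these additional visits may not be required".

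**The concern.** Sites work from the visit tables, and here the tables tell them to omit draws that the text requires. The secondary endpoint in section 8.3.2 counts subjects with any positive antibody result up to Day 169 and in three months of follow-up for double-blind discontinuers, and separately over the cumulative abatacept period plus follow-up. If sites resolve the conflict differently, ascertainment becomes uneven, and no analysis can recover a sample that was never drawn.

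The EOT note bears most on placebo-randomised subjects who stop open-label abatacept early. Their draws on Days 1, 85 and 169 all precede their first abatacept dose (Day 169 is a predose sample). Without an EOT draw, their first sample after abatacept exposure is the 28-day follow-up one. They remain evaluable through the 28- and 84-day draws of section 3.1.4. Abatacept-randomised subjects already have Days 85 and 169.

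Footnote d bears on double-blind discontinuers. One who attends Day 169 still gives a post-dose sample, but its time off drug depends on when dosing stopped.

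**Working it through.** The plan states no figure to reproduce. The check is a comparison of texts, followed by a count of whether the regular draws could stand in for the waived ones.

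**Comparison, EOT sample.** Table 5.1-3 note: none at EOT. Table 5.5.1-1: drawn at Day 365 or EOT. On the narrowest reading, the X keeps Day 365 for completers and the note removes only an early EOT draw. That still contradicts the EOT half of the Table 5.5.1-1 row.

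**Comparison, follow-up samples.** Sections 3.1.4 and 3.5 and the Table 5.1-2 note: the visit may be merged within ±14 days, but the sample is kept. Footnote d: the sample itself may be dropped, with no ±14-day condition. Sections 3.1 and 3.5 oblige discontinuers to keep attending double-blind visits, so footnote d's condition describes the very group that section 3.5 covers. Footnote a of Table 5.1-6 speaks of visits only and can be read as the merging rule, so that conflict is weaker.

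**Inputs for the count**
- Weekly dosing gives 24 possible last-dose days: L = 1, 8, ..., 162. Day 162 is the planned last double-blind dose.
- Fixed antibody draws after Day 1 (Table 5.1-2): D = 85 and 169.
- Tolerance of ±14 days, taken from the merging rule in section 3.1.4.
- Assumption: the 28- and 84-day samples are waived and the subject attends Days 85 and 169. Any Early Termination draw is left out.

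**84-day target.** A draw serves if 70 ≤ D − L ≤ 98.
- D = 85 needs L ≤ 15: Days 1, 8, 15 (3 days).
- D = 169 needs 71 ≤ L ≤ 99: Days 71, 78, 85, 92, 99 (5 days).
- Covered: 3 + 5 = 8. Not covered: 24 − 8 = **16 of 24**, or 15 of 23 without Day 162.
- If both draws move together by up to 3 days (the visit window), the count without Day 162 runs from 15 to 17 of 23. One to three days early, L must be at most 14 to 12 for the first draw (2 days) and between 70–68 and 98–96 for the second (4 days), so 23 − 6 = 17. One to three days late gives 3 + 4 = 7 covered, so 16.

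**28-day target.** A draw serves if 14 ≤ D − L ≤ 42.
- D = 85 needs 43 ≤ L ≤ 71 (5 days); D = 169 needs 127 ≤ L ≤ 155 (5 days).
- Not covered: 24 − 10 = **14 of 24**, or 13 of 23 without Day 162.

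**Both targets.** Only L = 71 qualifies: Day 85 is 14 days off drug and Day 169 is 98 days off.

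**Could a regular visit host the 84-day sample?** L + 84 exceeds 183 (Day 169 + 14) for L = 106 to 162, which is 9 of 24 days. For these there is no double-blind visit to merge with.

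**Any follow-up sample at all.** SAP section 6.1 starts the immunogenicity follow-up period at Day 22 after the last dose. From 169 − L ≥ 22, L ≤ 147. Days 148, 155 and 162 therefore have none: 3 of 24, or 2 of 23 without Day 162.

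**The case against.** **On the EOT note,** the X in the same row suggests that Day 365 stays for completers, so only early open-label stoppers are affected, and they still have the 28- and 84-day draws. Section 5.8.1.1 also points to section 5.5.1 as the governing schedule. The narrowing is fair, and the consequence described here is confined to that group. It does not remove the contradiction, and a site following the visit table would skip the draw.

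**On footnote d,** the wording is permissive, it opens by saying the samples should be collected, and several other places state one rule. Section 3.1 does use softer language for the merged sample. Still, only footnote d waives the sample without a timing condition.

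**On the counts,** footnote d could be read as lapsing once double-blind visits end. That would take out the 9 last-dose days from 106 to 162 and leave 7 (Days 22 to 64). Subjects stopping on those days still have two off-drug draws: 21 to 63 days off drug at Day 85 and 105 to 147 at Day 169. This is a reasonable reading, but a subject followed to Day 169 literally meets the footnote's condition. It is also true that ±14 days is a merging tolerance rather than an analysis window, that an Early Termination draw may add a sample soon after the last dose, and that the counts are of calendar days, not subjects.

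**On versions,** the SAP follows later amendments, with follow-up immunogenicity at 85 and 169 days, so its Day-22 rule is only an indicative yardstick here. Those amendments mention reconciling inconsistencies, but the documents do not show that these notes were corrected.

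**On importance,** no hypothesis test, sample size or primary analysis changes. That stands.

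**Conclusion.** The point holds: the protocol is wrong as written in two places. The EOT note contradicts the antibody schedule, at least for subjects who stop open-label treatment early. Footnote d waives samples that sections 3.1.4 and 3.5 require. If footnote d is followed, the fixed draws miss the 84-day target for 16 of 24 possible last-dose days and the 28-day target for 14 of 24. These figures assume that the waiver applies to anyone followed to Day 169, that the ±14-day tolerance is the yardstick, and that no Early Termination draw is counted. They say nothing about how many subjects would be affected, which the documents do not give. The effect is limited to a descriptive secondary safety endpoint. It should be corrected, because the samples are lost or mistimed at collection and the correction is nearly free.

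**What to change.** 1. Delete the EOT note from the PK and immunogenicity rows of Table 5.1-3, so that they match Table 5.5.1-1.
2. Reword footnote d of Table 5.5.1-1 and footnote a of Table 5.1-6: a follow-up visit falling within ±14 days of a scheduled double-blind visit may be merged with it, but the 28- and 84-day antibody samples must still be drawn.

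The cost is one table note (in two rows) and two footnotes. Every sample concerned is already scheduled elsewhere in the protocol, so no procedure is added.
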